#### 6.2.4 Protocol Deviations

#### 6.2.4.1 Relevant Protocol Deviations

The frequency table of relevant protocol deviations are provided as the number and percentage of subjects in deviation categories by as-randomized treatment group, zavegepant pooled, placebo pooled, and overall for the full analysis set. Results are shown by deviation type (eligibility, subject management), category, and subcategory in the order specified in Section 9.1. Results for all relevant protocol deviation categories and subcategories are displayed, even those with 0 counts, unless specified otherwise.

A by-subject listing of relevant protocol deviations is provided for the full analysis set. This includes deviation type, category, and subcategory, which are additional sorting variables.

## 6.2.4.2 Significant Protocol Deviations

The by-subject listing of significant protocol deviations is provided for the full analysis set, and is based on the Protocol Deviations CRF. This includes date deviation occurred, violation code, inclusion/exclusion number, and description, which are additional sorting variables. Significant protocol deviations are defined as those with a "yes" response to the question "Is the deviation significant?".

#### 6.2.5 Baseline Characteristics

Baseline characteristics include (1) demographics and other relevant baseline characteristics, (2) baseline disease characteristics (i.e., migraine history, cardiac and other risk factors, and efficacy during the OP), (3) medical history, and (4) non-study prior medications. These are detailed in Sections 6.2.5.1 through 6.2.5.4, respectively.

Tables of baseline characteristics are provided for the following analysis sets:

- Migraine analysis set: Baseline characteristics (1) and (2) by as-randomized treatment group, placebo pooled, and overall to support efficacy
- DBT safety analysis set: Baseline characteristics (1) through (4) by as-treated treatment group, zavegepant pooled, placebo pooled, and overall to support safety
- OL zavegepant safety analysis set: Demographics and other relevant baseline characteristics by OL zavegepant dose and overall to support OL zavegepant safety

The frequency cross table of randomization stratum (i.e., stable prophylactic migraine medication use through randomization [yes, no]) from IWRS versus actual data is provided for the full analysis set by treatment group and overall (see Section 6.2.5.4).

Baseline for a parameter (e.g., weight) is defined according to analysis set; refer to the Core SAP for details, including handling of ties on the same measurement date (entry date/time is the "earliest data creation time" variable in the raw CRF datasets). Note that the baseline value is independent of the baseline analysis visit defined in Table 5; the latter is used only in by-subject listings that display visit.

By-subject listings are provided for the enrolled analysis set for the following: demographics; medical history; and migraine history.

#### 6.2.5.1 Demographics and Other Relevant Baseline Characteristics

Refer to the Core SAP for the table of demographics and other relevant baseline characteristics. Other relevant characteristics also include the following categorical variables:

- Previous study participation (e.g., any study, BHV3500-201, BHV3500-301)
- Randomization stratum based on actual data stable prophylactic migraine medication use through randomization: yes, no (see Section 6.2.5.4).

#### 6.2.5.2 Baseline Disease Characteristics

#### **Migraine History**

Refer to the Core SAP for the table of migraine history.

#### **Cardiac and Other Risk Factors**

Refer to the Core SAP for the table of cardiac and other risk factors, which is provided only for the DBT safety analysis set.

## Migraine-related Event Days during the OP

The table of migraine-related event days per month during the OP is provided only for the migraine analysis set, and summarizes the following parameters descriptively as continuous or categorical variables during the OP analysis period:

- Migraine days per month by pain intensity (total; moderate or severe). Categories are < 6,  $\geq 6$ , < 8,  $\geq 8$ , < 12,  $\geq 12$ , < 15,  $\geq 15$ .
- Acute migraine-specific medication days per month. Categories are same as for migraine days per month above.
- Acute migraine medication days per month. Categories are same as for migraine days per month above.

See Sections 6.3.1 for migraine days per month, Section 6.3.2.2 for acute migraine-specific medication days per month, Section 6.3.3.6 for acute migraine medication days per month, and Section 7.2 for the OP analysis period.

Categories may be redefined or combined based on the availability of the data.

## 6.2.5.3 Medical History

The frequency table of medical history is provided by system organ class (SOC) and preferred term (PT), and displayed in descending order of overall frequency within SOC and PT.

## 6.2.5.4 Non-study Prior Medications

Frequency tables of the following non-study medications are provided by therapeutic class and preferred name:

- Current medications: all; acute migraine; prophylactic migraine
- Stable prophylactic migraine medications through randomization.

Medications are displayed in descending order of overall frequency within therapeutic class and preferred name. See Section 6.2.6.3.

Stable medications through randomization are defined as those taken > 12 weeks before informed consent and through randomization, i.e., (1) informed consent date – imputed medication start date > 84 days, and (2) IWRS randomization date ≤ imputed medication end date.

#### 6.2.6 Exposure

Analyses are based on as-treated treatment group to support safety, unless specified otherwise.

## 6.2.6.1 Study Medication

During the DBT Phase, study drug is zavegepant 100 mg, zavegepant 200 mg, or matching placebo daily; subjects take four (4) to eight (8) 25 mg SGCs daily, depending on their randomized treatment assignment.

During the OLE Phase, study drug is zavegepant 100 or 200 mg; subjects take four (4) to eight (8) 25 mg SGCs daily, depending on their randomized treatment assignment in the DBT Phase.

Study drug is dispensed in a wallet-type blister card with a unique wallet ID. Each wallet has 8 rows of 4 capsules for a total of 32 capsules. Sites report the wallet ID, study medication start date, study medication end date, and number of capsules taken on the IP Dosing CRF. Wallet IDs are 5 digits for DB study drug and 6 digits for OL zavegepant.

The kit type identifier associated with a wallet ID is DB zavegepant 100 mg, DB zavegepant 200 mg, DB placebo 100 mg, DB placebo 200 mg, OL zavegepant 100 mg, or OL zavegepant 200 mg, and is obtained by merging the IP Dosing CRF data with the DB study drug kit list file data and OL zavegepant kit list file data by wallet ID.

The by-subject listing of study drug is provided for the safety analysis set, and presents study medication start date, study medication end date, study day derived from study medication start

date, number of capsules taken  $\geq 0$ , wallet ID, and kit type identifier. The listing also displays DB study drug start and end dates, OL zavegepant start and end dates, displays study drug exposure parameters (time on DBT, time on OL zavegepant, time on DB or OL zavegepant), and identifies invalid wallet IDs. Valid DB wallet IDs are those in the DB study drug kit list file. Valid OL wallet IDs are those in the OL zavegepant kit list file. The listing is sorted by site-subject ID, study medication start date, study medication end date, and wallet ID.

## **DB Study Drug Exposure**

The table of DB study drug exposure is provided descriptively by treatment group, zavegepant pooled, and placebo pooled for the DBT safety analysis set, and summarizes the following parameters descriptively as continuous or categorical variables:

- Time on DB study drug (weeks), derived as (DB study drug end date DB study drug start date + 1)/7
- Time on DB study drug (weeks) categories:  $< 2, \ge 2$  to  $< 4, \ge 4$  to  $< 6, \ge 6$  to  $< 8, \ge 8$  to  $< 10, \ge 10$  to  $< 12, \ge 12$
- Cumulative DB study drug exposure (mg), derived by summing {number of days × number of capsules taken per day × dose} across records with complete study medication start date and valid DB wallet ID
  - Number of days for a record is derived as imputed study medication end date study medication start date + 1.
  - The dose is 25 mg if the kit type identifier is DB zavegepant 100 or 200 mg; otherwise, the dose is 0.
- Average DB study drug exposure (mg per day), derived as cumulative DB study drug exposure/time on DB study drug (days)
- Total DB study drug exposure (capsules) summed across all subjects, derived by summing cumulative DB study drug exposure across all subjects
- Total DB study drug exposure (patient-years), derived by summing (DB study drug end date
   DB study drug start date + 1)/365.25 across all subjects.

## **OL Zavegepant Exposure**

The table of OL zavegepant exposure is provided descriptively by OL zavegepant dose and overall for the OL zavegepant safety analysis set, and summarizes the following parameters descriptively as continuous or categorical variables:

- Time on OL zavegepant (weeks), derived as (OL zavegepant end date OL zavegepant start date + 1)/7
- Time on OL zavegepant (weeks) categories:  $\leq 12, \leq 24, \geq 24$
- Time on OL zavegepant milestone categories:

- $\circ$   $\geq$  3 months, defined as  $\geq$  11 weeks
- $\circ$   $\geq$  6 months, defined as  $\geq$  23 weeks
- $\circ$   $\geq$  1 year, defined as  $\geq$  51 weeks.
- Cumulative OL zavegepant exposure (mg), derived by summing {number of days × number of capsules taken per day × 25} across records with complete study medication start date and valid OL wallet ID
- Average OL zavegepant exposure (mg per day), derived as cumulative OL zavegepant exposure/time on OL zavegepant (days)
- Total OL zavegepant exposure (capsules) summed across all subjects, derived by summing cumulative DB exposure across all subjects
- Total OL zavegepant exposure (patient-years), derived by summing (OL zavegepant end date
   OL zavegepant start date + 1)/365.25 across all subjects.

## **DB** or **OL Zavegepant** Exposure

The table of DB or OL zavegepant exposure is provided descriptively by DB or OL zavegepant dose and overall for the DB or OL zavegepant safety analysis set, and summarizes the following parameters descriptively as continuous or categorical variables:

- Time on DB or OL zavegepant (weeks), derived as (DB or OL zavegepant end date DB or OL zavegepant start date + 1)/7
- Time on DB or OL zavegepant (weeks) categories:  $\leq 12, \leq 24, \geq 24$
- Time on DB or OL zavegepant milestone categories:
  - $\circ$   $\geq$  3 months, defined as  $\geq$  11 weeks
  - $\circ$   $\geq$  6 months, defined as  $\geq$  23 weeks
  - $\circ$   $\geq$  1 year, defined as  $\geq$  51 weeks
  - $\circ$  ≥ 15 months, defined as ≥ 63 weeks.
- Cumulative DB or OL zavegepant exposure (mg), derived as {number of days × number of capsules taken per day × 25} across records with complete study medication start date and kit type identifier of DB zavegepant 100 mg, DB zavegepant 200 mg, OL zavegepant 100 mg, or OL zavegepant 200 mg
- Average DB or OL zavegepant exposure (mg per day), derived as cumulative DB or OL zavegepant exposure/time on DB or OL zavegepant drug (days)
- Total DB or OL zavegepant exposure (capsules) summed across all subjects, derived by summing cumulative DB exposure across all subjects
- Total DB or OL zavegepant exposure (patient-years), derived by summing (DB or OL zavegepant end date DB or OL zavegepant start date + 1)/365.25 across all subjects.

## 6.2.6.2 Measurements of Treatment Compliance

## **DB** Treatment Compliance

DB treatment compliance categories are defined as follows for relevant protocol deviations (see Sections 6.2.4.1 and 9.1):

- DB study drug taken but not randomized
- DB capsule count compliance < 80% from DB study drug start to later of last scheduled DBT Phase visit or DB study drug end/OL zavegepant start. Capsule count compliance is derived as 100 × actual cumulative DB capsule count/required cumulative DB capsule count, where
  - Actual cumulative DB capsule count is derived by summing the {number of days × number of capsules taken per day} across records with complete study medication start date and valid DB wallet ID.
    - Number of days for a record is derived as imputed study medication end date study medication start date + 1.
  - Required DB cumulative capsule count is derived as {DB maxdate DB study drug start date + 1} × {required number of capsules per day}, where
    - DB maxdate is defined as the latest of the (1) scheduled Week 2, 4, 8, and 12/EOT visit dates, and (2) DB study drug end date. Scheduled visits are identified from visit labels from the Visit Date CRF, and therefore exclude those containing "unscheduled" in the visit label.
    - If DB maxdate  $\geq$  OL zavegepant start date, then DB maxdate is set to OL zavegepant start date -1 day.
    - The required number of capsules per day is 4 for subjects in the zavegepant 100 mg or matching placebo group, and 8 for subjects in the zavegepant 200 mg or matching placebo group.
- More than the required number of DB capsules per day taken on any 1 day. This is determined from either of the following:
  - Records with complete study medication start date, valid DB wallet ID, and number of capsules taken per day > required number of capsules per day.
  - Overlapping records with valid DB wallet ID (see Section 9.4).
- Incorrect DB study drug taken
  - All the time. Defined as as-treated treatment group not equal to as-randomized treatment group, i.e., either of the following:
    - Subjects randomized to zavegepant who took  $(1) \ge 1$  capsule from a DB placebo wallet, and (2) no capsules from a DB zavegepant wallet
    - Subjects randomized to placebo who took  $(1) \ge 1$  capsule from a DB zavegepant wallet, and (2) no capsules from a DB placebo wallet.

 At least once. Defined as (1) subjects randomized to zavegepant who took ≥ 1 capsule from a DB placebo wallet, or (2) subjects randomized to placebo who took ≥ 1 capsule from a DB zavegepant wallet.

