6.5 Early Discontinuation from the Study

Subjects MUST discontinue investigational product (and non-investigational product at the discretion of the investigator) for any of the following reasons:

- Withdrawal of informed consent (subject's decision to withdraw for any reason)
- Any clinical adverse event (AE), laboratory abnormality or intercurrent illness which, in the opinion of the investigator or sponsor, indicates that continued participation in the study is not in the best interest of the subject
- Pregnancy
- Termination of the study by Biohaven Pharmaceuticals
- Loss of ability to freely provide consent through imprisonment or involuntary incarceration for treatment of either a psychiatric or physical (e.g., infectious disease) illness

- Poor compliance with study procedures and visits, including poor completion compliance with evening reports in eDiary; poor compliance with study drug – see Schedule of Assessments Table 1 and Table 2.
- All subjects who discontinue in the DBT Phase early should comply with protocol specified DBT EOT procedures as outlined in Table 1. All subjects who discontinue in the OLE Phase early should comply with the protocol specified OLE EOT procedures as outlined in Table 2. The only exception to this requirement is when a subject withdraws consent for all study procedures or loses the ability to consent freely (i.e., is imprisoned or involuntarily incarcerated for the treatment of either a psychiatric or physical illness).

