## **OL Zavegepant Treatment Compliance**

OL zavegepant treatment compliance categories are defined as follows for relevant protocol deviations (see Sections 6.2.4.1 and 9.1):

- OL zavegepant capsule count compliance < 80% from OL zavegepant start to later of last scheduled OLE Phase visit or OL zavegepant end. Capsule count compliance is derived as 100 × actual cumulative OL zavegepant capsule count/required cumulative OL zavegepant capsule count, where
  - Actual cumulative OL zavegepant capsule count is derived by summing the {number of days × number of capsules taken per day} across records with complete study medication start date and valid OL wallet ID.
  - Required cumulative OL zavegepant capsule count is derived as {OL maxdate OL zavegepant start date + 1} where
    - OL maxdate is defined as the latest of the (1) scheduled Weeks 14, 16, 20, 24, 28, 32, 36, 40, 44, 48, 52, 56, 60, and 64/EOT visit dates, and (2) OL zavegepant end date. Scheduled visits are identified from visit labels from the Visit Date CRF, and therefore exclude those containing "unscheduled" in the visit label.
    - The required number of capsules per day is based on the DB treatment group; see "DB Treatment Compliance".
- > 1 OL zavegepant capsule taken on any 1 day. This is determined from either of the following:
  - Records with complete study medication start date, valid OL wallet ID, and number of capsules taken per day > required number of capsules per day.
  - Overlapping records with valid OL wallet ID (see Section 9.4).
- OL zavegepant start date before DB study drug end date. Defined as OL zavegepant study drug start date ≤ DB study drug end date.
- OL zavegepant taken but DB study drug never taken. Defined as nonmissing OL zavegepant start date and missing DB study drug start date.

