  - ≤ 5 migraine days, if originally consented to Protocol Version 3 or lower
  - $0 \le 7$  migraine days, if originally consented to Protocol Version 4 or higher
  - $0 \ge 19$  headache days, if originally consented to Protocol Version 3 or lower
  - $\circ$   $\leq$  14 headache days, if originally consented to Protocol Version 4 or higher
  - No headache-free days, if originally consented to Protocol Version 4 or higher. A
    headache-free day is defined as a day of eDiary efficacy data that is not a headache day
    of total pain intensity (see Section 9.2.6).
  - $\circ$  ≤ 23 days of eDiary efficacy data (see Section 9.2.2).

These are assessed during the 28-day OP analysis period (see Section 7.2). Migraine days and headache days are absolute, not prorated to 28 days per month (see Sections 9.2.5 and 9.2.6), and of total pain intensity.

Protocol version for original consent is from the Inclusion/Exclusion CRF.

Relevant subject management protocol deviations include the following categories:

- Randomization stratum discrepancies between IWRS and actual data, defined as any of the following subcategories:
  - o IWRS randomization stratum of yes, but no stable prophylactic migraine medication taken through randomization
  - IWRS randomization stratum of no, but stable prophylactic migraine medication taken through randomization.

See Section 6.2.5.4 for the definition of non-study stable medication through randomization.

- Prophylactic migraine medication usage issue, defined as any of the following subcategories:
  - Prophylactic migraine medication started or stopped from 12 weeks before informed consent to randomization. Defined as informed consent date − 84 days ≤ imputed nonstudy medication start or end date ≤ IWRS randomization date.
  - > 1 prophylactic migraine medication taken on or after informed consent. "> 1" is defined as > 1 unique preferred name.
- DB study drug dosing issue, defined as any of the following subcategories (see Section 6.2.6.2):
  - DB study drug taken but not randomized
  - o More than the required number of DB capsules taken on any 1 day
  - DB capsule count compliance < 80% from DB study drug start to later of last scheduled DBT Phase visit or DB study drug end/OL zavegepant start
  - Incorrect DB study drug taken

- OL zavegepant dosing issue, defined as any of the following subcategories (see Section 6.2.6.2):

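### Capsule-count compliance treats the days between the last dose and the end-of-treatment visit as missed dosing, so a fully adherent early discontinuer is reported as a < 80% deviation when that gap exceeds one quarter of the time on drug

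*SAP*

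**What the plan says.** SAP 6.2.6.2 (DB Treatment Compliance) defines capsule-count compliance as actual over required capsules, times 100.

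- Numerator: "Actual cumulative DB capsule count is derived by summing the {number of days × number of capsules taken per day", taken over valid dosing records. It stops growing at the last dosing record.
- Denominator: "Required DB cumulative capsule count is derived as {DB maxdate DB study drug start date + 1", multiplied by the daily requirement. "The required number of capsules per day is 4 for subjects in the zavegepant 100 mg or matching placebo group"; it is 8 in the 200 mg and matching placebo groups.
- End of the window: "DB maxdate is defined as the latest of the (1) scheduled Week 2, 4, 8, and 12/EOT visit dates", with the double-blind drug end date as the other candidate. The only cap moves it to the day before open-label dosing starts.

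On use, the SAP states that "DB treatment compliance categories are defined as follows for relevant protocol deviations". Section 9.1 lists, as a double-blind dosing issue, "DB capsule count compliance < 80% from DB study drug start to later of last scheduled DBT Phase visit", the window extending to drug end or open-label start. Section 6.2.4.1 tabulates and lists these deviations for the full analysis set.

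The open-label rule is parallel: "OL maxdate is defined as the latest of the (1) scheduled Weeks 14, 16, 20", and so on to Week 64/EOT, or the open-label drug end date.

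Protocol 6.5 lists reasons for which study drug must be stopped and adds: "All subjects who discontinue in the DBT Phase early should comply with protocol specified DBT EOT procedures as outlined in Table 1". Table 1 gives the EOT visit no timing relative to the last dose.

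**The concern.** A subject taken off drug as Protocol 6.5 requires has no further doses to take, but the denominator keeps adding 4 or 8 capsules a day until the EOT visit. The open-label cap gives no relief, because Protocol 4.3.3 bars early discontinuers from the extension. A fully adherent subject can therefore appear in the deviation table and listing as having taken under 80% of required capsules.

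The row then mixes ordinary discontinuation with real under-dosing. SAP Version 8 removed the treatment compliance tables and listing, so this category is the remaining planned output on low capsule-count compliance. It also disagrees with the exposure table in SAP 6.2.6.1, whose time on drug ends at the drug end date.

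**Working it through.** **Plan's own figure.** The SAP states no compliance percentage for an early discontinuer. The related figure it does give is the dosing example in section 9.4. Summing days × capsules over the records with capsules taken gives 3×4 + 4×4 + 3×8 + 1×4 = 56 capsules on 10 dosing days, 3 of them above the required 4. All three figures match the SAP, so the numerator is understood as intended.

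**Formula.** Let d be days on drug with every capsule taken, g the days from last dose to EOT visit, and c the required capsules per day (4 or 8).

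- Actual = d × c
- Required = (d + g) × c
- Compliance = 100 × d/(d + g); c cancels, so both dose levels behave alike
- Below 80% when d/(d + g) < 0.80, that is, when g > d/4

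The documents do not fix g, so it is shown as a range:

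| d (days) | Smallest g flagged | Compliance there | g = 3 | g = 7 | g = 14 |
|---|---|---|---|---|---|
| 7 | 2 | 77.8% | 70.0% | 50.0% | 33.3% |
| 14 | 4 | 77.8% | 82.4% | 66.7% | 50.0% |
| 28 | 8 | 77.8% | 90.3% | 80.0% | 66.7% |
| 42 | 11 | 79.2% | 93.3% | 85.7% | 75.0% |
| 56 | 15 | 78.9% | 94.9% | 88.9% | 80.0% |
| 70 | 18 | 79.5% | 95.9% | 90.9% | 83.3% |

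Exactly 80.0% is not flagged, and g = 0 always gives 100%.

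**One illustration, on an assumption.** Suppose the EOT visit is held at the next scheduled visit (Day 15, 29, 57 or 86) and the first dose is on Day 2, as Protocol 4.3.2 indicates. The windows are then 14, 28, 56 and 85 days. A perfect taker is flagged for d = 1–11, 15–22, 29–44 and 57–67: 11 + 8 + 16 + 11 = 46 of 85 possible values of d (54%). The other 39 are not flagged. This counts possible stopping times and does not predict how many subjects are affected.

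**Contrast with the exposure table.** A zavegepant 100 mg subject who doses perfectly for 14 days, with an EOT visit 4 days after the last dose, has average exposure 14 × 4 × 25 / 14 = 100 mg per day, yet compliance 14/18 = 77.8%.

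**Open-label rule.** Its required-count line omits the capsules-per-day factor, but a sub-bullet supplies it. Read that way, the same condition applies. With an assumed gap of 30 days, 120 open-label days give 120/150 = 80.0%, not flagged, so at that gap only shorter exposures are affected.

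**After the fix.** Ending the window at the drug end date makes the required count d × c, and compliance is 100% for any d and g.

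**The case against.** The window is deliberate: the category label itself says that it runs to the later of the visit and drug end. The visit term does useful work, because it catches subjects who stop taking capsules while still assigned to treatment. Poor compliance is itself a ground for discontinuation (Protocol 6.5 and 7.4). If every non-completer's window ended at the last capsule, a subject who took capsules for 7 days, refused drug until day 28 and was then discontinued for poor compliance would move from 7/28 = 25% to 100%. This stands, and it limits the fix. It does not justify counting days after a required stop as missed doses.

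It is also fair that little depends on the figure. Efficacy data end at the double-blind drug last date, no analysis set uses capsule compliance, and the disposition table and study drug listing let a reader separate stopping from missed doses.

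Three stronger readings are tempting, and the documents do not support them:

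- That early discontinuers in general are misreported. A prompt EOT visit or a late stop leaves compliance at or above 80%.
- That every open-label subject affected by the December 2023 termination is flagged. The same g > d/4 condition applies, and the SAP does not say how long before their EOT visits those subjects stopped dosing.
- That the table will show a false imbalance between arms. The documents give no discontinuation rates by arm and no EOT gaps.

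**Conclusion.** The concern holds under a stated condition. A subject who took every capsule and then permanently stopped is reported as a < 80% dosing deviation when the gap to the EOT visit exceeds one quarter of the days on drug. After short exposure a small gap is enough: 2 days after 7 days of dosing, 4 days after 14. The number of subjects affected cannot be derived, because the gap is not fixed. The effect is confined to the relevant-deviation table and listing.

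This assumes that the Core SAP, which was not available, contains no overriding rule; section 6.2.6.2 refers to none. The point is worth correcting because the rule can label a fully adherent subject as a dosing deviation and the repair is cheap. It does not bear on the validity of the efficacy estimates.

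**What to change.** For capsule-count compliance only, end the required-capsule window at the double-blind drug end date (or the open-label zavegepant end date) when the Subject Status CRF records that the phase was not completed for a reason other than poor compliance or loss to follow-up. Keep the scheduled-visit date for completers, for subjects discontinued for non-compliance or lost to follow-up, and for subjects whose completion response or reason is missing. Leave DB maxdate unchanged for eDiary usage compliance, which shares it, and align the category wording in SAP 9.1.

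The cost is a short SAP edit, a second end date for the capsule calculation and minor programming. SAP 6.2.3.3 and 6.2.3.4 already use reasons for non-completion. The documents do not list the CRF reason codes, so it must be checked that poor compliance and loss to follow-up are separately identifiable.

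The downside is that a subject who stopped capsules some time before being recorded as discontinued for another reason would count as compliant up to the last capsule. That subject would still appear as a non-completer in the disposition table.
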